### 3.6 EXAMINATION OF SUBGROUPS

Subgroup analyses will be conducted on the primary and exploratory aims for the following groups:

- Gender: male and female.

For the subgroup analyses, all completers in each subpopulation will be randomly split into training data set and testing data set with a 1:1 ratio, stratified by WHO ASSIST risk levels. The cut-off threshold values will be selected using similar methods as described in Aim 1 for each subgroup and validated using similar methods as described in Aim 2, with the testing set for the corresponding subgroup. We will compare the selected threshold values and their discriminative ability between subgroups, see **Table 6** for details. *It should be noted* that the study is *not* designed to detect certain agreement level between metrics with high statistical power within any subgroup.

**Table 6. Summary table that compares discrimination ability of NS metrics with established cut-off threshold between 2 gender subgroups, with WHO ASSIST as gold standard.**

		Female	Male	Overall
AUC of ROC	Low risk vs Moderate risk			
	Moderate risk vs high risk			
NS Metric cut-off values	Low risk vs Moderate risk			
	Moderate risk vs high risk			
Validation of selected cut-off values				
Kappa coefficient				
Spearman Correlation Coefficient				
Goodman and Kruskal's Gamma				
Kendall rank correlation coefficient				
Odds ratio from ordinal logit regression				

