10.8 Inclusion of Women and Minorities

The study sites should aim and take steps to enroll a diverse study population. Noted in section 2.3 of the study appendix, based on our previous research on this topic, we anticipate 57% of our sample will be female, and 43% will be male. Assessments captured (i.e., TAPS Tool alcohol subscale) are specified for male vs. female respondents. We also anticipate our study sample will approximate the racial/ethnic distributions of the local areas in which the recruitment stores operate. If difficulty is encountered in recruiting an adequate number of women and/or minorities, the difficulties involved in recruitment will be discussed in national conference calls and/or face-to-face meetings and plans to correct these difficulties will be put into place.

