The study will be powered to the least prevalent but most severe condition among potential patients. Based on the allocation ratio of the national rate of prescription opioid use disorder (POUD) among those prescribed opioid medications in the last year, the prevalence of Poud is 2.1%. A sample of approximately 1,523 (32 positive group) achieves 97.68% power to detect a difference of 0.2 between the area under the ROC curve (AUC) under the null hypothesis of 0.5 and the alternative hypothesis of 0.7 using a two-sided z-test at a significance level of 0.050.

The Completer Population (both training and testing set) will be used to assess the overall discrimination ability of NS metric.

*To determine cut-point threshold values for NS total score:*

The objective is to select the optimal cut-points threshold for NS metric to define low, moderate and high risk groups. We will use a hybrid framework where we can make use of the data driven methods to support the clinician's final decision making. Only the training data set will be used in this portion of analysis.

In the first step, the solution space (a subset of optimum choices of cut-point threshold values) will be identified with the following grid search approach: for each pair of risk groups, for example, low risk vs moderate risk, calculate the following performance measurements for each possible cut-point threshold value:

- Sensitivity (SE)

$$SE = \frac{\text{True Positive Rate}}{\text{True Positive Rate} + \text{False Negative Rate}}$$

- Specificity (SP)

$$SP = \frac{\text{True Negative Rate}}{\text{True Negative Rate} + \text{False Positive Rate}}$$

- Positive Predictive Value (PPV): probability that the risk level is present (based on WHO ASSIST) when the result with NS metric is positive.
- Negative Predictive Value (NPV): probability that the risk level is not present (based on WHO ASSIST) when the test result with NS metric is negative.
- Youden's index:

$$\text{Youden's Index} = SE + SP - 1$$

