	Figure 6.2.3	CP	NS metric ROC curve for discriminating high risk vs low risk opioid misuse patients (defined by POMI)
	Figure 6.2.4	CP	NS metric ROC curve for discriminating high risk vs low risk opioid misuse patients (defined by POMI), by gender
	Table 6.2.5	CP	Summary of AUC of ROC curve, for NS metric vs POMI
	Table 6.2.6	CP	Summary of AUC of ROC curve, for NS metric vs POMI by gender
	Table 6.2.7	CP	Summary of Kappa Coefficient and Correlation Analysis Results, NS metric vs POMI
	Table 6.2.8	CP	Summary of Kappa Coefficient and Correlation Analysis Results, NS metric vs POMI, by gender

Section	Table/Figure #	Analysis Population	Title
Results for Exploratory Aim 2 – explore association between NS metric vs OESWD	Table 6.2.9	CP	Summary of ordinal logit regression results, NS metric vs POMI
	Table 6.2.10	CP	Summary of ordinal logit regression results, NS metric vs POMI, by gender
	Table 6.3.1	CP	Confusion Table for NS metric with established cut-off threshold vs OESWD
	Table 6.3.2	CP	Confusion Table for NS metric with established cut-off threshold vs OESWD, by gender
	Figure 6.3.3	CP	NS metric ROC curve for discriminating high risk vs low risk opioid misuse patients (defined by OESWD)
	Figure 6.3.4	CP	NS metric ROC curve for discriminating high risk vs low risk opioid misuse patients (defined by OESWD), by gender
	Table 6.3.5	CP	Summary of AUC of ROC curve, for NS metric vs OESWD
	Table 6.3.6	CP	Summary of AUC of ROC curve, for NS metric vs OESWD by gender
	Table 6.3.7	CP	Summary of Kappa Coefficient and Correlation Analysis Results, NS metric vs OESWD
	Table 6.3.8	CP	Summary of Kappa Coefficient and Correlation Analysis Results, NS metric vs OESWD, by gender
Results for Subgroup Comparison	Table 6.3.9	CP	Summary of ordinal logit regression results, NS metric vs OESWD
	Table 6.3.10	CP	Summary of ordinal logit regression results, NS metric vs OESWD, by gender
Results for Subgroup Comparison	Table 7.1	CP	Summary table that compares selected cut-off threshold values with NS metric between 2 gender subgroups.
	Table 7.2	CP	Summary table that compares discrimination ability of NS metrics with established cut-off threshold between 2 gender subgroups, with WHO ASSIST as gold standard.
	Table 7.3	CP	Summary table that compares discrimination ability of TAPS tool between 2 gender subgroups, with WHO ASSIST as gold standard.

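### Cut-points chosen separately in women and men are compared with no measure of error, although each training half holds only about 9 high-risk women and 7 high-risk men

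*SAP*

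**What the plan says.** SAP 3.5 plans every analysis overall and within each sex, and names sex differences in the selected cut-points as one purpose. SAP 3.6 splits the completers of each sex 1:1 into training and testing sets and then states: "The cut-off threshold values will be selected using similar methods as described in Aim 1 for each subgroup". Each sex's thresholds are validated in that sex's own testing set. The results are then compared: "We will compare the selected threshold values and their discriminative ability between subgroups". Table 6 has female and male columns for the cut-off values, and Appendix 1 adds a shell for this alone, Table 7.1: "Summary table that compares selected cut-off threshold values with NS metric between 2 gender subgroups".

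The selection rule in SAP 3.5 has two steps. A solution space of thresholds with high Youden's index is found in the training half. A clinician then chooses within it so that sensitivity (SE) and specificity (SP) are in balance.

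SAP 3.6 warns that the study was not designed for high power on agreement within a subgroup. It gives no interval, bootstrap or test for a threshold or for the female-male difference. The ordinal model in Aim 2 has sex as a covariate but no NS-by-sex interaction.

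**The concern.** A cut-point is an estimate, and one chosen by maximising Youden's index on few positives is an unstable one. The planning figures are for both sexes together: "A sample of approximately 1,523 (32 positive group) achieves 97.68% power". Dividing 32 patients by sex and then by training half leaves single figures in each cell that fixes a high-risk threshold.

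Two such thresholds will differ even if the NS metric behaves identically in women and men. A table showing, say, 430 for one sex and 500 for the other (invented values) gives the reader no means of telling a sex effect from sampling error. The purpose of the study is to give pharmacists usable thresholds, so a chance gap could be taken as support for sex-specific ones. The SAP's warning does not prevent this, because it concerns power for agreement and not the stability of a selected threshold.

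**Working it through.** **1. The plan's own figure.** Inputs from SAP 3.5: 32 positives and 1,523 − 32 = 1,491 negatives; AUC "under the null hypothesis of 0.5 and the alternative hypothesis of 0.7"; "using a two-sided z-test at a significance level of 0.050". Binormal variance with equal SDs: A = √2·Φ⁻¹(AUC), R = 1,491/32 = 46.6, f = exp(−A²/4)/√(4π), g = −A·exp(−A²/4)/√(16π), V = f²(1 + 1/R + A²/2) + g²(1 + R)/(2R).

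- AUC 0.5: V = 0.0813, standard error = √(0.0813/32) = 0.0504.
- AUC 0.7: A = 0.742, V = 0.0826, standard error = 0.0508.
- Power = Φ[(0.20 − 1.96 × 0.0504)/0.0508] = 97.68%.

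The stated figure reproduces. It applies to all 32 positives together.

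**2. Patients behind each sex-specific threshold.** SAP 3.5: "the prevalence of Poud is 2.1"%. Protocol 10.8: "we anticipate 57% of our sample will be female". The split is 1:1 within sex (SAP 3.6).

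- High-risk women per half: 1,523 × 0.57 × 0.021 / 2 = 9.1.
- High-risk men per half: 1,523 × 0.43 × 0.021 / 2 = 6.9.
- Moderate risk is 17.1% − 2.1% = 15.0%. That gives 65.1 women and 49.1 men per half as comparators for the moderate-versus-high cut.

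**3. Size of a chance gap.** NS scores for both sexes were drawn from the same distributions (2,000 simulated studies per cell). Counts were binomial, with 434 women and 327 men per training half. The moderate-versus-high threshold was chosen in each sex by two rules: the maximum Youden value, and the value with SE closest to SP within the top 10% of Youden values, as a stand-in for the clinician step. The SD and shape are assumptions, because the documents give only the 000-999 scale.

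| Normal SD | AUC | Max Youden: median gap | over 100 | Balanced: median gap | over 100 |
|---|---|---|---|---|---|
| 100 | 0.70 | 55 | 22% | 27 | 3% |
| 100 | 0.80 | 46 | 14% | 25 | 2% |
| 150 | 0.70 | 84 | 42% | 42 | 15% |
| 150 | 0.80 | 70 | 34% | 38 | 10% |
| 200 | 0.70 | 112 | 54% | 64 | 30% |
| 200 | 0.80 | 92 | 46% | 60 | 25% |

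With counts fixed at 9 and 7, the maximum-Youden figures for AUC 0.70 / 0.80 are 20% / 13%, 39% / 31% and 53% / 46%. Runs agree within two or three points, so the ranges are best read as about 15-53% for maximum Youden and about 2-28% for the balanced rule. The women's and men's solution spaces fail to overlap at all in 2-29% of these studies. Wider shapes give larger gaps: for scores uniform on the scale, 62-71% (maximum Youden) and 46-56% (balanced) exceed 100 points.

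**4. Precision of SE by sex in the testing half.** Exact 95% intervals: 7 of 9 detected gives 0.40-0.97; 6 of 7 gives 0.42-1.00.

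**The case against.** The strongest reply has four parts.

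*The 100-point gap is not a finding of the documents.* A reader might infer from the small counts that chance gaps above 100 NS points would be common. That needs an NS spread the documents do not give, and a pure maximum-Youden pick that the SAP does not use. At SD 100, or with a balancing second step at SD 150 or below, such gaps are uncommon (2-22% across those cells). This stands. The second step reduces the noise only if one rule is applied alike to both sexes, however, and the SAP writes none down. The median gap is still 25 points or more in every cell.

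*Common cut-points by sex may already be planned.* A reader of SAP 3.6 alone might infer that the plan never checks whether one set of cut-points works equally in women and men. Shells 4.2 and 4.4 in Appendix 1 report the testing set by gender at the cut-off established in Aim 1, and SE and SP can be read from the confusion table in 4.2. Because SAP 3.5 and 3.6 also select cut-points by sex, the shells do not settle which set is meant. That is an ambiguity, not an omission.

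*Readers will see more than bare thresholds.* By-sex AUCs in all completers, by-sex grid searches, and SE and SP plots across the solution space are planned, and would hint at a flat Youden curve. This stands in part: none of them measures the error of the difference shown in Tables 6 and 7.1.

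*The remedy meets the same limit.* With 9 women and 7 men, Fisher's exact test has about 29% power for a true SE of 0.9 in women against 0.5 in men. This is true, and it is a reason to show intervals and claim little. It is not a reason to show thresholds without them.

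**Conclusion.** The point holds in a limited form. The separate selection, the direct comparison without a measure of error, and the counts of about 9 and 7 all follow from the documents. With no true sex difference, the high-risk thresholds would typically differ by tens of NS points (median about 25 to 110). Gaps over 100 points occur in about 15-53% of studies under maximum Youden and about 2-28% under a balancing second step. These sizes rest on an assumed normal NS distribution with SD 100 to 200, an AUC of 0.70 to 0.80, and the planned prevalence and sex mix.

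One might go further and ask that the sex-specific high-risk cut-point be dropped. The documents do not require that: SAP 3.5 and 3.6 name the comparison as a purpose, and Protocol 9.6 commits to analyses by sex. What is missing is a statement of its error.

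**What to change.** - **SAP 3.6, Tables 6, 7.1 and 7.2:** give a bootstrap confidence interval for each sex-specific threshold and for the female-male difference, and label the comparison descriptive. Write the second-step choice as a rule applied alike to both sexes, so that each resample can repeat it.
- **Shells 4.2 and 4.4:** state that the overall Aim 1 cut-points are applied to women and men in the testing half. Report SE and SP by sex with exact intervals.
- **AUC:** by-sex values in all completers are already planned (Table 3.6 under the Aim 1 results). Add a confidence interval for the female-male difference. This uses every high-risk patient and needs no threshold.
- **Caveat in SAP 3.6:** extend it from agreement to the comparison of thresholds.

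The cost is some SAP wording and a little more computation on data already collected. The intervals will be wide, and SE by sex will remain imprecise. The planned sex-specific analyses are all kept.

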### 3.7 MISSING DATA

The completer population, defined as participants who complete all opioid outcome score contributing items on the WHO ASSIST and TAPS tool, will be used for the main analysis. Completers also must have a NS metric score. As a result of the one-time cross-sectional nature of this study, participant attrition is not a concern. Rubin's multiple imputation approach will be used to impute missing covariates but missing outcome data will not be imputed.

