9.5 Missing Data and Dropouts

This study does not include follow-up assessments, and all study assessments will be completed during the electronic health assessment survey. Missing data and dropouts are expected to be relatively minimal. Nonetheless, the analysis will determine the extent of missing data for all study variables and explore differences in missing data by age, gender, and race/ethnicity. The completer population, defined as participants who complete opioid outcome score contributing items on the WHO ASSIST and TAPS tool, will be used for the main analysis. Completers also must have NS metric scores. Multiple imputation will be conducted for missing covariates, but missing key outcome data will not be imputed. See CTN 0093 Statistical Analysis Plan for details.

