### **2.1.2 COMPLETER POPULATION**

A participant is considered as a completer if all of the participant's electronic Case Report Forms (eCRFs) have been completed, although it is possible that some questions on the eCRFs may not be answered. The completer population will be used as the main analysis population.

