### **2.2.2 WHO ASSIST**

The WHO ASSIST opioid use risk domain will be used as the gold standard to which the NS metric will be compared. The WHO ASSIST opioids domain is a continuous indicator on a 0-20 scale, with the 0-0.5 range representing low risk, the 0.5-14.5 range representing moderate risk, and the 14.5-20 range representing high risk. The WHO ASSIST has demonstrated criterion, construct, concurrent, and discriminant validity.

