### **3.3 DISPOSITION**

The number and percentages of screened and enrolled subjects as well as subjects who complete all eCRFs will be presented based on ENR.

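### The main analysis population has two non-nested definitions, and the stricter one excludes patients with valid NS and ASSIST scores over TAPS items that Aims 1 and 2 do not need

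*SAP*

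**What the plan says.** Four places bear on who is analysed.

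- **SAP 2.1.2** makes a participant a completer once all of their eCRFs are completed, "although it is possible that some questions on the eCRFs may not be answered". It does not mention an NS score. It then states: "The completer population will be used as the main analysis population".
- **SAP 3.3** follows the same idea. It reports, among others, "subjects who complete all eCRFs will be presented based on ENR".
- **SAP 3.7** gives the same name and role to participants who "complete all opioid outcome score contributing items on the WHO ASSIST and TAPS tool", and adds: "Completers also must have a NS metric score". Missing covariates are to be multiply imputed; missing outcomes are not.
- **Protocol 9.5** agrees with SAP 3.7: "participants who complete opioid outcome score contributing items on the WHO ASSIST and TAPS tool", and "Completers also must have NS metric scores".

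For the primary comparison, SAP 2.2.2 states: "The WHO ASSIST opioid use risk domain will be used as the gold standard to which the NS metric will be compared". TAPS is analysed in Exploratory Aims 1 and 2 (SAP 3.5).

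**The concern.** The completer set is used for the overall AUC, the 1:1 training and testing split stratified by ASSIST risk level, the gender subgroups and nearly all the table shells. Two programmers working from this SAP could build different primary datasets, and the choice between them could be made after the data are seen.

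The TAPS condition raises a second problem. Protocol 11.4 lets participants decline any item, and the TAPS opioid items ask about drug misuse, so declining may be related to risk. Excluding a patient whose NS score and ASSIST opioid score are both known gives up usable primary data. The high-risk group is where that could hurt: 32 patients are expected, about 16 in each half after the split.

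**Working it through.** **Step 1. Apply the definitions to the same patients.**

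| Patient | SAP 2.1.2 | SAP 3.7 and Protocol 9.5 | Usable in the NS-ASSIST comparison? |
|---|---|---|---|
| All forms completed, NS score and ASSIST opioid items present, one TAPS opioid item declined | In | Out | Yes |
| NS score and all ASSIST and TAPS opioid items present, an unrelated form (e.g. pain) unfinished | Out | In | Yes |
| All forms completed, no NS score | In | Out | No |
| All forms completed, an ASSIST opioid item declined | In | Out | No, if the score cannot be formed |

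The first two rows show that neither set contains the other. In the last two rows, 2.1.2 admits patients who cannot be analysed; the last kind could not even be placed in an ASSIST stratum for the split.

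**Step 2. Trace what Aims 1 and 2 use (SAP 3.5).** The AUC, cut-point search, confusion matrix, kappa and Spearman analyses use the NS metric and the ASSIST opioid risk level only. The Aim 2 ordinal regression adds sex, pain, general health, depression and a substance use history term that points to Table 1 without naming an instrument. Table 1 includes TAPS, so a TAPS score could enter there. It would then be a covariate, and SAP 3.7 imputes missing covariates.

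**Step 3. Reproduce the plan's power.** Inputs from SAP 3.5: N = 1,523, 32 positives (so 1,523 − 32 = 1,491 negatives), AUC 0.5 against 0.7, two-sided α = 0.05, stated power 97.68%.

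Power = Φ[(0.2 − 1.96·√V₀)/√V₁], with V₀ and V₁ the AUC variances at 0.5 and 0.7.

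- Obuchowski binormal variance: 97.7%, which matches.
- Hanley-McNeil variance: 97.1%, close to the stated figure and slightly more conservative. It is used in Step 4.

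Hanley-McNeil: V(A) = [A(1−A) + (n₁−1)(Q₁−A²) + (n₀−1)(Q₂−A²)]/(n₁n₀), with Q₁ = A/(2−A) and Q₂ = 2A²/(1+A). At A = 0.7, Q₁ = 0.5385 and Q₂ = 0.5765. With 32 and 1,491, √V₀ = 0.0516 and √V₁ = 0.0523, so power = Φ(1.890) = 0.971 and the 95% half-width is 1.96 × 0.0523 = 0.103.

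**Step 4. Vary the loss.** The documents give no TAPS non-response rate, so the losses are assumptions. Negatives are held at 1,491.

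| High-risk patients lost | Positives left | Power | AUC 95% half-width |
|---|---|---|---|
| 0 | 32 | 0.971 | 0.103 |
| 2 | 30 | 0.962 | 0.106 |
| 5 | 27 | 0.943 | 0.112 |

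On the Obuchowski variance, an even 10% loss across all risk groups (N = 1,371, 29 positives) gives 96.5%, about one point below 97.7%. A large drop needs heavy, concentrated loss: if half the high-risk patients went and 2% of the rest (16 positives, 1,461 negatives), power would be 80.5%.

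**The case against.** The strongest defence has four parts.

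- **The conflict is narrow.** SAP 3.7 and Protocol 9.5 agree, and both are item-level statements in the missing-data sections. They could be read as saying which of the unanswered questions allowed by 2.1.2 disqualify a patient. This would settle the declined-item and missing-NS cases, but not the patient with an unfinished unrelated form, nor the eCRF-based count in 3.3.
- **A common set may be intended.** TAPS validation is the protocol's secondary objective, and a single set keeps denominators equal across analyses. That is possible, but neither document gives this reason, and equal denominators would not justify discarding valid pairs from the primary analysis.
- **Missingness should be low.** Protocol 9.5 expects little missing data, every item needs a response even if it is a refusal (Protocol 11.4), and payment depends on few or no missing values (Protocol 8.7). This stands and limits the size of the effect.
- **The remedy is partial.** Someone unwilling to answer drug-use questions may decline ASSIST opioid items too, and would still be excluded. This also stands: the patients recovered are those who answer every ASSIST opioid item and then decline a TAPS one.

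A reader might go further and infer that primary power is at risk, or that the cut-points will be biased. The documents support neither. The losses are assumed, and power stays at 94% even with five high-risk patients lost. A reader might also infer from the numbered list in the study schema that patients who stop early have already answered the ASSIST. The list gives the survey's contents and does not state an order of administration.

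**Conclusion.** The point holds as an inconsistency in the main analysis population together with an unnecessary exclusion. It decides who enters the primary analysis, so it should be settled before the dataset is derived. The case does not rest on power: under an assumed loss of 2 to 5 of 32 high-risk patients, power falls by 0.9 to 2.8 percentage points and the AUC half-width grows by 0.003 to 0.009. Selective declining could also shift observed prevalence, predictive values and the chosen cut-points, but nothing in the documents allows that to be quantified. It would be too strong to say that Aims 1 and 2 can never use TAPS; the regression's substance use term leaves room for it, as a covariate that would be imputed if missing.

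**What to change.** Use one definition in SAP 2.1.2, 3.3 and 3.7 and in Protocol 9.5:

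- For Aims 1 and 2, include every eligible, non-duplicate participant with an NS score and all ASSIST opioid score items, whether or not other forms are finished.
- Apply the duplicate check to every included record. Protocol 6.3.2.2 and 8.7 place it after survey submission, so a survey that was not fully submitted could otherwise enter unchecked.
- Require TAPS items only for analyses that use TAPS.
- Keep the planned multiple imputation of covariates.
- Report how many participants each criterion excludes.

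The cost is wording in both documents, a duplicate check on incomplete surveys, and slightly different denominators between the NS-ASSIST and TAPS tables.
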